3. PRIMARY AND SECONDARY VARIABLES

3.1 Safety

The primary outcome measure for the study is the number and proportion of patients with AESI. Pre-defined Medical Dictionary for Regulatory Activities (MedDRA) preferred terms groupings will be used to identify AESI.

'On treatment' will be defined as assessments between date of first dose and 90 days following last dose inclusive.

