3.1.1 Adverse Events (AEs)

AEs and SAEs will be collected throughout the study, from time of signature of informed consent and up to 90 days after the last dose of immunotherapy agents (ie, the last dose of durvalumab or tremelimumab). MedDRA (using the latest or current MedDRA version) will be used to code the AEs. AEs will be graded according to the National Cancer Institute (NCI) Common Terminology Criteria for AEs (CTCAE Version 4.03).

A treatment emergent adverse event (TEAE) is an AE with an onset date or a pre-existing AE worsening following the first dose of study treatment through to 90 days after the last dose of immunotherapy agents. For the durvalumab + tremelimumab modules, in the event of the components being administered separately, then date of first dose/last dose will be considered as the earliest/latest dosing date of either component. Any AE occurring before study treatment (i.e. before the administration of the first dose on Study Day 1) will be included in the AE listings, but will not be included in the summary tables (unless otherwise stated). These will be referred to as 'pre-treatment'. However, any AE occurring before the administration of the first dose on Study Day 1 that increases in severity after the first dose will be regarded as treatment emergent and thus will be included in the majority of summary tables.

For patient level summaries, if more than one AE is coded to the same PT for the same patient, the patient will be counted only once in summaries using the most serious grading on causal relationship to study treatment.

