3.1.2 Secondary Safety Endpoints

3.1.2.1 Treatment exposure

Exposure will be defined as follows:

Total (or intended) exposure of study treatment

• Total (or intended) exposure = [earliest of (last dose date where dose > 0 mg +28 days, death date, DCO date] – first dose date + 1

Actual exposure of study treatment

• Actual exposure = intended exposure – total duration of dose interruptions, where intended exposure will be calculated as above.

Dose reductions are not permitted per section 6.9.1 of the core CSP. The actual exposure calculation makes no adjustment for any dose reductions that may have occurred.

Exposure will also be measured by the number of cycles received. For each immunotherapy agent a cycle corresponds to one dose of treatment. A cycle will be counted if treatment is started even if the full dose is not delivered.

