4. ANALYSIS METHODS

4.1 General principles

No hypothesis testing is planned for this single arm study. Each module will be summarised separately.

The general principles as mentioned below will be followed throughout the study:

- Descriptive statistics will be used for all variables, as appropriate, and will be presented separately for each module. Descriptive safety and efficacy data from the STRONG study may be utilized as supporting evidence for health authority considerations.
- Continuous variables will be summarized by the number of observations, mean, standard
 deviation, median, minimum, and maximum. For log transformed data it is more
 appropriate to present geometric mean, coefficient of variation (CV), median, minimum
 and maximum. Categorical variables will be summarized by frequency counts and
 percentages for each category.
- Unless otherwise stated, percentages will be calculated out of the population total.
- Exact CIs for proportions will be calculated using the Clopper-Pearson method.
- For percentiles of survival times based on the Kaplan-Meier method (eg, median survival), CIs will be calculated using the default method available in the SAS LIFETEST procedure (ie, the Klein and Moeschberger extension of the Brookmeyer-Crowley method).
- For point-estimates of survival based on the Kaplan-Meier method (eg, for OS at 12 months), CIs will be calculated using the default method available in the SAS LIFETEST procedure (ie, using Greenwood's estimate of standard error and a log-log transformation).
- For continuous data the mean and median will be rounded to 1 additional decimal place compared to the original data. The standard deviation will be rounded to 2 additional decimal places compared to the original data. Minimum and maximum will be displayed with the same accuracy as the original data.
- For categorical data, percentages will be rounded to 1 decimal place.
- SAS® version 9.3 or higher will be used for all analyses.

Baseline will be the last assessment of the variable under consideration prior to the intake of the first dose of study treatment.

All data collected will be listed.

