4.2.1 Safety data

Data from all cycles of treatment will be combined in the presentation of safety data. The following sections describe the planned safety summaries. However, additional safety tables may be required to aid interpretation.

Adverse Events

All AEs will be summarised descriptively, in terms of number of patients (n) and percentage of patients (%) reporting the event by MedDRA system organ class (SOC) and preferred term (PT). The majority of the AE summaries, unless stated otherwise, will be based on TEAEs.

Any adverse events that occur prior to dosing or starting more than 90 days after discontinuing treatment will be presented in a separate summary by SOC and PT.

All reported AEs will be listed along with the date of onset, date of resolution (if AE is resolved) and investigator's assessment of severity and relationship to study drug.

Summary information (the number and percent of patients by SOC and PT) will be tabulated for:

- All TEAEs
- All TEAEs causally related to study medication (as determined by the reporting investigator)
- TEAEs with CTCAE grade 3 or higher
- TEAEs with CTCAE grade 3 or higher, causally related to study medication (as determined by the reporting investigator)
- TEAEs by outcome
- TEAEs with outcome of death
- TEAEs with outcome of death causally related to study medication (as determined by the reporting investigator)
- All treatment-emergent SAEs
- All treatment-emergent SAEs causally related to study medication (as determined by the reporting investigator)
- All treatment-emergent SAEs by maximum NCI CTCAE grade
- TEAEs leading to discontinuation of study medication
- TEAEs leading to discontinuation of study medication, causally related to study medication (as determined by the reporting investigator)
- TEAEs leading to hospitalization
- TEAEs leading to dose interruption of study medication
- Other significant TEAEs
- Other significant TEAEs causally related to study medication (as determined by the reporting investigator)
- Designated medical events
- Infusion reaction TEAEs (as determined by the reporting investigator)

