As well as the overall summary of the number and percentage of patients in each SOC/PT category, an overall summary of the number of episodes in each SOC/PT category will be presented. In addition, a truncated AE table of most common AEs and another table showing most common AEs with CTCAE grade 3 or higher, showing all events that occur in at least 5% of patients overall will be summarised by PT, by decreasing frequency. This cut-off may be modified after review of the data. When applying a cut-off (ie, x %), the raw percentage

will be compared to the cut-off, no rounding will be applied first (i.e., an AE with frequency of 4.9% will not appear if a cut-off is 5%).

An overall summary of the number and percentage of patients in each AE category (Any AE, Any AE causally related to treatment, Any AE of CTCAE grade 3 or higher etc...) will be presented.

Each AE event rate (per 100 patient years) will also be summarised by PT within each SOC for the output summarising all AEs. For each preferred term, the event rate is defined as the number of patients with that AE divided by the total drug exposure of patients at risk of AE. The denominator is the total duration of treatment (in years) across all patients calculated as the sum total (of all patients) of days from first dose to the earlier of the date of first onset of the event or the last day of study medication.

As a part of the trial's Disclosure Record to the National Institute of Health (NIH), the following tables will be produced

- TE non-serious AEs
- TE non-serious AEs causally related to study medication (as determined by the reporting investigator)
- TE non-serious AEs occurring in >5% of Patients
- TE non-serious AEs occurring in >5% of patients causally related to study medication (as determined by the reporting investigator)
- Summary of the number of episodes of treatment-emergent SAE in each SOC/PT category
- Number of subjects enrolled per age group as per EU categories.

Fluctuations observed in CTCAE grades during study will be listed for those TEAEs which are CTCAE > 3.

In addition, all AEs will be listed.

Adverse events of special interest (primary outcome)

Summaries of treatment emergent AESI by category and PT will include number (n) and percentage (%) of patients who have:

- At least one treatment-emergent AESI
- At least one treatment-emergent AESI by outcome
- At least one treatment-emergent AESI leading to treatment interruption or discontinuation

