- Death related to disease under investigation ONLY, as determined by investigator (including deaths occurring within 90 days after last dose of study medication and deaths occurring after the 90 days post dosing window)
- TEAEs with outcome of death ONLY
- AEs with outcome of death ONLY and onset date falling after 90 days follow-up period
- Deaths related to disease under investigation, as determined by the investigator, and with TEAE with outcome of death
- Deaths related to disease under investigation, as determined by the investigator, and with AE with outcome of death and onset date falling after 90 days follow-up period
- Deaths that occurred 90 days after last dose, and unrelated to AE (ie no AE with outcome of death) or disease under investigation

- Patients with unknown reason for death
- Other deaths

Summary of long term tolerability

To assess long term tolerability, provided that there are a sufficient number of patients with events to warrant it (\geq 10 events), prevalence plots and cumulative incidence plots will be presented for each AESI category and for any other events considered important after review of the safety data.

A prevalence plot provides information on the extent to which the events may be an ongoing burden to patients. The prevalence at time t after first dose of study treatment is calculated as the number of patients experiencing the event divided by the number of patients receiving study treatment or in safety follow-up at time t; generally, t is categorised by each day after dosing. The prevalence will be plotted over time. Multiple occurrences of the same event are considered for each patient but a patient is only counted in the numerator whilst they are experiencing one of the occurrences of the event. The raw cumulative incidence is the actual probability that a patient will have experienced their first occurrence of the event by a given time point.

Treatment exposure

The following summaries related to study treatment will be produced for the SS:

- Total exposure, actual exposure, and total number of cycles received will be summarised separately for the initial treatment phase and the re-treatment phase. For the modules with combination therapy, those summaries will be carried out once for each drug separately and once for combination separately from monotherapy.

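### The adverse event rate per 100 patient-years counts onsets up to 90 days after the last dose but stops its person-time when study medication stops

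*SAP*

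**What the plan says.** Three parts of the SAP together define the rate.

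- **Denominator.** Under Adverse Events in section 4.2.1, each patient contributes "days from first dose to the earlier of the date of first onset of the event or the last day of study medication". The rate is the number of patients with the preferred term divided by the sum of this time.
- **Numerator.** The rate paragraph sets no onset window. Section 4.2.1 opens with a default: "The majority of the AE summaries, unless stated otherwise, will be based on TEAEs". Section 3.1.1 defines a treatment-emergent event as one that starts or worsens "following the first dose of study treatment through to 90 days after the last dose of immunotherapy agents". Besides pre-dose events, only those "starting more than 90 days after discontinuing treatment will be presented in a separate summary by SOC and PT" are moved out of the main tables, so onsets in the 90 days after treatment stay in.
- **End of the treatment period.** Section 3.1 says that on treatment "will be defined as assessments between date of first dose and 90 days following last dose inclusive". Section 3.1.2.1 ends exposure at the earliest of "last dose date where dose > 0 mg +28 days", death and data cut-off. The rate paragraph uses neither date and does not say which calendar date its own end point means.

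For the prevalence plot in the same section, the number of patients with the event is "divided by the number of patients receiving study treatment or in safety follow-up at time t", so there the two windows agree.

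**The concern.** An incidence rate needs events and time at risk from the same period. Here the events can come from a window up to 90 days longer than the time. The result is neither the rate over the treatment-emergent window nor the rate while on drug. The error runs in one direction, upwards, and grows as treatment gets shorter.

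The rate is a supporting, descriptive output. It still matters, because section 4.1 says "Descriptive safety and efficacy data from the STRONG study may be utilized as supporting evidence for health authority considerations", and a reader of a published rate per 100 patient-years will assume that its two parts match.

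**Working it through.** The SAP states no numerical event rate, so there is no figure to reproduce. The check compares the definitions and then sizes the gap under stated assumptions.

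**1. Algebra (no assumptions).** For one preferred term, let T_on be the pooled event-free time up to the person-time cut-off and T_off the pooled event-free time from there to the end of the treatment-emergent window. Let E_on and E_off be the first onsets in each period.

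- SAP rate = (E_on + E_off) / T_on
- Rate over the treatment-emergent window = (E_on + E_off) / (T_on + T_off), so the SAP rate is too high by the factor 1 + T_off/T_on. This applies to every non-zero rate.
- On-drug rate = E_on / T_on, so the factor is 1 + E_off/E_on. This applies only to terms with at least one late onset.

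If person-time ends at the last infusion, a patient with a single infusion contributes about one day of time but can contribute an event for 90 days more.

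**2. One worked case.** Assume a true rate of 10 per 100 patient-years, constant through the window, with no death or cut-off. Take 84 days from first to last dose, which is four doses at the 4-weekly interval. The window is 84 + 90 = 174 days.

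- Numerator: 1 − exp(−0.10 × 174/365.25) = 0.0465
- Person-time to last dose: [1 − exp(−0.10 × 84/365.25)] / 0.10 = 0.2274 years, giving 0.0465/0.2274 = 20.5 per 100 patient-years
- Person-time to last dose + 28 days (112 days): 0.3020 years, giving 15.4
- Person-time to last dose + 90 days: 10.0

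The same formula with 28, 168 and 336 days from first to last dose gives 41.6, 15.2 and 12.5 (last dose), or 20.9, 13.1 and 11.6 (+28 days). The ratio hardly depends on the event rate: at 84 days and last dose it is 2.07, 2.05 and 2.00 for true rates of 2, 10 and 30.

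**3. Variable treatment length, with deaths (simulation).** Assumptions: true hazard 30 per 100 patient-years; number of doses geometric with the median shown; window of last dose + 90 days, cut by death (none, or a median of 120 or 60 days after the last dose). Ranges cover the two medians in each row and the three death assumptions. Entries are rates per 100 patient-years under constant hazard.

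| Median doses | Time ends at last dose | Time ends at last dose + 28 days | Matched windows |
|---|---|---|---|
| 2–3 | 45–68 | 37–49 | 30 |
| 4–5 | 39–48 | 34–40 | 30 |
| 8–9 | 35–38 | 32–35 | 30 |

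With time ending at the last dose, 34–56%, 23–37% and 14–22% of counted patients in the three rows have their onset after their person-time has closed.

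**4. Sensitivity.**

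- If 20% are still on treatment at cut-off and so have no off-drug time, the last-dose column becomes 42–61, 37–44 and 34–37.
- If the hazard halves after the last dose, the factor against the treatment-emergent window barely moves (1.5–2.3, 1.3–1.6 and 1.2–1.3 for last dose), because it depends on person-time.
- Under that halved hazard, the factor against an on-drug rate ending at last dose + 28 days is 1.13–1.37, 1.08–1.19 and 1.04–1.09.

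**The case against.** The strongest reply is that this is an exposure-adjusted rate: the SAP calls the denominator drug exposure, and an exposure period may properly differ from a safety-observation period. That is fair as a target, but an on-drug rate needs on-drug events in the numerator, and the paragraph does not impose that.

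A second reply is that the treatment-emergent numerator is inferred. The default covers most AE summaries, not all, and the paragraph speaks only of the AE. A reader could take it to mean onsets during exposure, which would match. The inference stands as such. It is the natural reading, because nothing in the paragraph departs from the default, and taking the words literally as all reported AEs would not remove the mismatch.

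Third, the SAP has related date rules. Section 3.1.2.2 uses the last recorded administration when treatment is stopped between cycles or during a delay, and the treatment exposure part of section 4.2.1 uses the cut-off date for patients still on treatment at the OS analysis. These narrow the candidates for the end date. They are not tied to the rate, and neither the last administration nor the 28-day extension reaches 90 days.

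Fourth, the largest figures need short treatment, time closed at the infusion day and an undiminished hazard off drug. That is true. The 28-day reading uses the SAP's only explicit exposure formula and gives smaller figures.

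Last, the consequence is limited. The AESI counts and exact intervals, the other n (%) tables, the Kaplan–Meier summaries and the prevalence plots do not use this denominator, and there is no comparator. Nothing says that this particular rate will be submitted. This stands and limits the weight of the point.

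**Conclusion.** The concern holds. On its natural reading the rate mixes a numerator running to 90 days after the last dose with person-time that ends 90 days earlier, or 62 days earlier (90 − 28) under the exposure definition. The bias is upward under either reading.

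The direction follows from the definitions. The size does not, because the documents give no treatment duration, post-treatment survival or off-drug hazard. Over the assumptions tried, the factor runs from about 1.04 (median 8–9 doses, 28-day reading, halved off-drug hazard, on-drug target) to about 2.3 (median 2–3 doses, last-dose reading, treatment-emergent target). The primary AESI proportions are not affected. This should be fixed before the output is programmed, but it does not threaten the study's main conclusions.

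**What to change.** Choose one target and state both halves of it.

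- **Treatment-emergent rate.** State that the numerator is patients with a treatment-emergent event, and end each patient's person-time at the earliest of first onset, last dose + 90 days, death and data cut-off. This agrees with the window used for the other AE tables.
- **On-drug rate.** Count only onsets within the exposure window of section 3.1.2.1, and end person-time at the earlier of first onset and the end of that window.

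Either choice is acceptable. In both cases the present end point in the rate paragraph should be replaced by a defined date. The cost is one sentence in the SAP and one changed line of programming. AE onset, dosing and death dates are already collected, so no new data are needed.

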6.3.3 Variables

The following variables will be collected for each AE:

- AE (verbatim)
- The date when the AE started and stopped
- The maximum CTCAE grade reported
- Changes in CTCAE grade (report only the maximum CTCAE grade for a calendar day)
- Whether the AE is serious or not
- Investigator causality rating against the IPs (yes or no)
- Action taken with regard to IPs
- Administration of treatment for the AE
- Outcome

In addition, the following variables will be collected for SAEs:

- Date the AE met criteria for SAE
- Date the Investigator became aware of the SAE
- Seriousness criteria
- Date of hospitalization
- Date of discharge
- Probable cause of death
- Date of death
- Whether an autopsy was performed
- Causality assessment in relation to study procedure(s)
- Causality assessment in relation to other medication, as explained in Section 6.3.4
- Description of the SAE

The grading scales found in the revised NCI CTCAE version 4.03 will be utilized for all events with an assigned CTCAE grading. For those events without assigned CTCAE grades, the recommendation in the CTCAE criteria that converts mild, moderate, and severe events into CTCAE grades should be used. A copy of the CTCAE version 4.03 can be downloaded from the Cancer Therapy Evaluation Program website (http://ctep.cancer.gov).

It is important to distinguish between serious and severe AEs. Severity is a measure of intensity whereas seriousness is defined by the criteria in Section 6.2 and the Additional Safety Information in APPENDIX A. An AE of severe intensity need not necessarily be considered serious. For example, nausea that persists for several hours may be considered severe nausea, but not a SAE unless it meets the criteria shown in Section 6.2 and APPENDIX A. On the other hand, a stroke that results in only a limited degree of disability may be considered a mild stroke but would be a SAE when it satisfies the criteria shown in Section 6.2 and APPENDIX A.

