In addition, there are certain circumstances in which durvalumab and tremelimumab should be permanently discontinued (see Section 3.9 of this protocol and the Dosing Modification and Toxicity Management Guidelines).

Following the first dose of IP, subsequent administration of durvalumab and tremelimumab can be modified based on toxicities observed as described in the Dosing Modification and Toxicity Management Guidelines. These guidelines have been prepared by the Sponsor to assist the Investigator in the exercise of his/her clinical judgement in treating these types of toxicities. These guidelines apply to AEs considered causally related to durvalumab monotherapy and the durvalumab + tremelimumab combination therapy regimen by the reporting Investigator.

Dose reductions are not permitted. In case of doubt, the Investigator should consult with the Study Physician.

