- At least one treatment-emergent serious AESI
- At least one treatment-emergent AESI by maximum NCI CTCAE grade
- At least one treatment-emergent AESI causally related to study medication
- At least one treatment-emergent AESI with fatal outcome
- At least one treatment-emergent AESI which required additional treatment with steroids, immunosuppressants and hormone replacement therapy
- Laboratory findings, vital signs and other safety parameters associated with AESI will be summarised as part of the AESI outcome measures.

Length of intervention with steroids, immunosuppressants and/or hormone replacement therapy for AESIs will be calculated based on treatment start and stop dates. Total treatment

times will then be combined for each patient and summarised for patients experiencing at least one treatment-emergent AESI.

The exact 95% CIs around the incidence estimates will also be reported for each AESI type.

A summary of total duration (days) of AESI will be provided. For ongoing AESI, the date of death or data cut-off will be imputed as end date.

Immuno-mediated adverse events

Summaries of treatment-emergent imAEs by AESI category and PT will include number (n) and percentage (%) of patients who have:

- At least one treatment-emergent imAE
- At least one treatment-emergent imAE by outcome
- At least one treatment-emergent imAE leading to treatment interruption or discontinuation
- At least one treatment-emergent serious imAEs
- At least one treatment-emergent imAE by maximum NCI CTCAE grade
- At least one treatment-emergent imAE causally related to study medication
- At least one treatment-emergent imAE with fatal outcome

Subgroup analyses

Subgroup analyses will be conducted for the summary of TEAEs in the following subgroups of the SS:

- Sex (male versus female)
- Age at baseline: <65 vs 65-74 vs ≥75 years of age). This will be determined from the date of birth (BRTHDAT in the DM domain) and baseline visit (VIS_DAT in the VISIT domain) on the eCRF. Patients with a partial date of birth (ie for those countries where year of birth only is given) will have an assumed date of birth of 1st Jan [given year]). Patients with a missing age value will be included using the mean age and categorised accordingly.
- Race: Asian vs non-Asian
- ECOG performance status at baseline: 0-1 vs 2
- Tumor histology: Urothelial (i.e. TCC) vs non-urothelial

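### The AESI and imAE summaries pool dose interruption with permanent discontinuation, so no planned category-level summary shows how many patients stopped treatment because of a given category

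*SAP*

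**What the plan says.** SAP section 4.2.1, under the AESI (primary outcome) subheading, introduces its list with "Summaries of treatment emergent AESI by category and PT will include number (n) and percentage (%) of patients who have". The only entry on study treatment is "At least one treatment-emergent AESI leading to treatment interruption or discontinuation". The imAE list in the same section has the matching entry "At least one treatment-emergent imAE leading to treatment interruption or discontinuation". The other AESI entries cover any event, outcome, seriousness, maximum CTCAE grade, causality, fatal outcome, treatment of the event with steroids, immunosuppressants or hormone replacement, and associated laboratory and vital-sign findings. None isolates permanent discontinuation.

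The general adverse event part of section 4.2.1 treats the two consequences separately, as "TEAEs leading to discontinuation of study medication" and "TEAEs leading to dose interruption of study medication". The level of those tables is set by "Summary information (the number and percent of patients by SOC and PT) will be tabulated for", so they are not organised by AESI category.

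SAP section 3.1.1.1 says that at interim and final analysis imAEs are found by preferred-term selection together with a programmed search for events that needed steroids, immunosuppressants or hormone replacement.

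Protocol section 6.3.3 lists "Action taken with regard to IPs" among the variables recorded for every adverse event. Protocol section 6.9.1 states "Dose reductions are not permitted".

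**The concern.** A held dose and a permanent stop mean different things to a reader of a safety study. The protocol separates them in practice: section 4 lets dosing be delayed and resumed, while section 3.9.1 identifies permanently discontinued patients and moves them to follow-up. Because reductions are ruled out, a hold and a stop are the main dosing consequences an AESI can have, and the AESI and imAE rows merge them.

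A category that mostly causes short holds and one that mostly ends treatment can therefore print the same percentage. The study exists to characterise AESIs, so the number of patients in each category whose treatment ended is a figure many readers will look for in these tables. The question is whether it can be obtained from some other planned summary.

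**Working it through.** **Step 1. Inputs.** Planned size of Module A: 600 to 1200 (SAP 1.3). Interval method: Clopper-Pearson (SAP 4.1). Row definitions: SAP 4.2.1. The documents give no expected rate for the pooled row, so 5% is assumed, with 2% and 10% as a range.

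**Step 2. Check of the interval method.** For x patients out of n, the lower limit is the 2.5% quantile of Beta(x, n − x + 1) and the upper limit is the 97.5% quantile of Beta(x + 1, n − x). For 60/1200 this gives 3.84% to 6.39%, and for 30/600 it gives 3.40% to 7.06%. SAP Table 1 prints 3.8-6.4 and 3.4-7.1 at 5% incidence, so the method reproduces.

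**Step 3. What the pooled row alone tells.** Let P be the pooled count and D the number permanently discontinued in a category. The row gives only 0 ≤ D ≤ P.

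| n | P (assumed 5%) | D = 0 | D = P/2 | D = P |
|---|---|---|---|---|
| 600 | 30 | 0.00% (95% CI 0.00 to 0.61) | 15 = 2.50% (1.41 to 4.09) | 30 = 5.00% (3.40 to 7.06) |
| 1200 | 60 | 0.00% (0.00 to 0.31) | 30 = 2.50% (1.69 to 3.55) | 60 = 5.00% (3.84 to 6.39) |

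With assumed pooled rates of 2% or 10% at n = 1200 (24 or 120 patients), D may be anything from 0 to 24 or from 0 to 120.

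**Step 4. What the preferred-term tables add for AESIs.** AESI categories are groups of preferred terms. For term j, let d_j be the patients in the discontinuation table and i_j those in the interruption table. One patient may have several terms, so

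- largest d_j ≤ D ≤ sum of d_j, and D cannot exceed P;
- D ≥ P − (sum of i_j), because every pooled patient who did not stop must have been interrupted.

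The count is exact if only one term contributes. It is also exact in the pure cases: if all d_j are 0 then D = 0, and if all i_j are 0 then D = P. In mixed cases it is only bounded. Assumed example at n = 1200 with P = 60: two terms each show 15 discontinuations, and the interruption counts sum to at least 60 − 15 = 45, so the second bound does not tighten the first. Then D lies between 15 (1.25%, 95% CI 0.70 to 2.05) and 15 + 15 = 30 (2.50%, 1.69 to 3.55).

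**Step 5. What they add for imAEs.** The general tables count every treatment-emergent event with a given term, whether or not it meets the medication condition in SAP 3.1.1.1. Each d_j is then only an upper limit on the imAE discontinuations for that term, even when a single term contributes. The lower limit for the category is the larger of 0 and (pooled imAE count − sum of i_j), and will often be 0.

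**Step 6. Is the pooled reading right?** In the same section the SAP writes two entries where it wants two tables. One joined entry in the AESI and imAE lists most naturally means one combined row.

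**The case against.** The strongest reply is that little is missing.

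- **Overall discontinuation is planned.** The all-event tables give discontinuation and interruption separately, and the treatment-exposure summaries report interruptions due to adverse events on their own. A reader might infer that the result cannot be set against the protocol's figure of about 10% of durvalumab monotherapy patients discontinuing because of an adverse event (section 1.3.2.1). That inference fails: the figure covers any adverse event, and its counterpart is planned.
- **Secondary objective 2 is met.** It concerns interruption and discontinuation due to treatment-emergent events generally, not by AESI category. The plan does not leave it unanswered.
- **The primary outcome is untouched.** It is the number and proportion of patients with an AESI (SAP 3.1), and the stated objective does not name dosing action.
- **The extreme cases can be recovered.** A category with only holds and a category with only stops can be told apart from the preferred-term tables, as Step 4 shows.
- **The lists are open and nothing is lost.** The SAP allows further safety tables and lists all collected data. Table shells are not among the documents, so the row might be programmed as two.

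The first four replies stand and limit the point. The last does not remove it. A permission to add tables commits to nothing, and a hand count from listings is not a pre-specified result. Nor do the preferred-term tables give category counts when several terms contribute, or any imAE count.

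**Conclusion.** The point holds as a reporting gap confined to the AESI and imAE summaries. As written, no planned category-level summary shows how many patients permanently stopped treatment because of a given AESI or imAE category. For AESIs the planned preferred-term tables bound the number and sometimes fix it exactly; for imAEs they supply little more than an upper limit. From the pooled row alone, the discontinuation rate lies anywhere between zero and the pooled rate: 0.0% to 5.0% in the assumed 5% example.

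A reader might infer that discontinuation is missing from the report altogether, or that the primary analysis is compromised. The documents support neither. The overall and preferred-term discontinuation figures are planned. The primary incidence estimate, its interval and the sample size do not change, and no hypothesis is tested.

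The conclusion rests on reading the joined entry as one row, which the SAP's own wording elsewhere favours but which the table shells could settle. The rates in the illustration are assumptions.

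**What to change.** In both the AESI and the imAE lists of SAP section 4.2.1, replace the joined entry by three rows, by category and preferred term:

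- events leading to dose interruption;
- events leading to permanent discontinuation;
- events leading to either.

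State that a patient counts in every row that applies, and that the rows are derived from the action-taken variable in Protocol section 6.3.3. In combination modules, show discontinuation by drug, because tremelimumab can stop while durvalumab continues (Protocol 1.4). This assumes that the action is recorded separately for each drug, which the protocol does not spell out and which should be checked against the case report form.

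The cost is a wording change and a few extra table rows. No new data, visits or analyses are needed.
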